is desired in the current trial, a higher QD dose can be administered at the investigator's discretion and in consultation with the sponsor. The dose can be increased up to 4 mg QD, in patients with an absolute weight of >50 kg, and up to 5 mg QD in adult patients with an absolute weight of >60 kg. These dose levels have been investigated previously in trial RM-493-026. Adult patients exposed to these higher dose levels should be monitored closely via additional unscheduled visits or telephone calls to assess safety and tolerability. For patients who escalate to 4 or 5 mg QD, the dose level should be reduced to 3 mg and 4 mg if their absolute weight decreases to \leq 50 kg and \leq 60 kg, respectively. The maximum dose of setmelanotide is limited by absolute body weight (kg) in order to maintain exposure to excipients in the setmelanotide formulation at a lower level than those currently approved for other commercially available medicinal products (see Section 3.2 for further details).

Overall, the expected benefit–risk assessment supports continued evaluation of setmelanotide in these rare patient populations with high unmet medical needs.

Refer to the Investigator Brochure for data regarding setmelanotide administration at doses up to 5 mg.

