8.1. Sample Size Estimation

The primary objective of this trial is to evaluate long-term safety and tolerability in patients with various rare genetic, syndromic, or acquired forms of obesity impacting the MC4R pathway after completing planned setmelanotide treatment in a previously completed index protocol. All patients who complete an index protocol and meet eligibility criteria can enroll in this trial. Thus, sample size estimation and power analyses are not relevant.

Given the rarity of these genetic and acquired diseases of the MC4R pathway, estimated power for exploratory endpoints such as expected will not be provided, and efficacy will be only summarized.

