8.4. Statistical Methods

Statistical methods, populations and approaches to missing data will be outlined in the SAP.

As these patient populations are extremely rare, efforts will be made to keep all patients in the trial, and all data collected, even if outside of visit windows, will be included in all analyses of endpoints. No missing data will be imputed, analyses will be carried out on all available data.

With respect to the exploratory endpoints, no adjustment for multiplicity will be included for the many patient populations in this trial as these different populations are included in this trial only for administrative convenience.

AEs will be coded by using the most current version of Medical Dictionary for Regulatory Activities (MedDRA) and summarized by system organ class and preferred term for the number and percent of AEs reported, the number of patients reporting each AE, and the number of patients with any AE.

Analyses of AEs will be performed for those events that are considered treatment-emergent, where treatment-emergent is defined as any AE with onset after the administration of study drug through the end of the trial, specifically, 30 days after the last dose of setmelanotide, or any event that was present at baseline but worsened in severity or was subsequently considered drug-related by the investigator through the end of the trial.

A by-patient AE data listing including onset and resolution dates, verbatim term, preferred term, treatment, severity, relationship to treatment, action taken, and outcome will be provided.

Safety data including laboratory evaluations and vital signs assessments will be summarized by time of collection. In addition, change from baseline to any post-dose values will be summarized for vital signs and clinical laboratory results. Frequency of patients with abnormal safety laboratory results will be tabulated.

Safety and efficacy data from both the index and extension trial may be combined to evaluate long-term safety and efficacy outcomes on a patient specific and population basis.

It is planned that analyses may be completed once all patients within each sub-population/cohort have completed at least 1 year of this extension protocol, data have been cleaned and finalized, and the database is locked for assessments in this first year. Additional supplemental analyses will be conducted on a yearly basis for patients who continue in the trial (for up to 7 years).

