11. APPENDICES

11.1. Injection Site Evaluations

Injection sites will be assessed at the timepoints outlined in the SOA (Table 1), and in the setting of any injection site reaction adverse experience. This assessment will consider severity and measurement (length and width if applicable) of any instance of erythema, edema, induration, itching, pain/tenderness or other relevant findings.

An example assessment form is shown below:

Reaction	NONE	Mild	Moderate	Severe	Measurement (if applicable)
Erythema*1					
Edema*					
Induration ^{*1}					
Itching					
Pain or Tenderness*					
Other:					

Local Skin Tolerability Assessment	Local	Skin	Tolerabili	ity Assessment
------------------------------------	-------	------	------------	----------------

* If present, region will be measured, length and width as appropriate.

In the event of severe erythema, defined as ≥10 cm, and/or induration of the injection area of the size of ≥10 cm and in the presence of fever defined as ≥38°C, or based on the investigator's clinical judgement, the investigator should contact the sponsor and discuss therapeutic management of the patient and potential temporary drug discontinuation.

Initials: _____

11.2. Guidance for Monitoring Potential Treatment-Related Dermatological Changes and Suggested Criteria for Discontinuation of Dosing

In clinical trials conducted with setmelanotide, skin hyperpigmentation (tanning), primarily noted on sun exposed areas, was reported during the first 7-14 days of treatment at clinical doses. In Phase 1/2 clinical studies, hyperpigmentation appeared uniform, and in most instances, returned to baseline within 30 days of discontinuing study drug. Some patients also noted changes in hair color as well. Facial hyperpigmentation on the muzzle and periorbital region was seen in the 14-day, 28-day, and 13-week toxicology studies in cynomolgus monkeys, with improvement or resolution seen by the end of the recovery period.

The investigator will identify a dermatologist to serve as a consultant for the investigative site. The dermatologist will receive training in trial procedures and the effects of setmelanotide prior to evaluating patients.

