3.12. Visit Windows

It is expected that all visits should occur according to the protocol schedule. All data will be tabulated per the evaluation visit as recorded on the CRF even if the assessment is outside of the visit window. If the evaluation visit is missing in the database but there are data from an unscheduled or additional visit that is inside the visit window, the data from the unscheduled or additional visit will be used in data summaries. All available data will be listed for each subject.

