4.5.3. Injection Site Evaluations

Injection site evaluations will be measured as shown in the SOA (Table 1-2) and will be summarized by visit according to severity (none, mild, moderate, severe) and type of reaction: erythema, edema, induration, itching, pain or tenderness, or other reaction. For subjects reporting more than one occurrence of the same type of reaction, the most severe reaction will be used for the summary.

A by-subject listing will be provided for all injection site evaluations and will also include measurement (if applicable).

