4.5.4. Laboratory Data

Clinical laboratory values will be expressed using the International System of Units (SI). Values will be summarized using raw, change and percent change from extension study baseline for

each clinical laboratory parameter. Clinical laboratory parameters include hematology, chemistry, and urinalysis.

Shift tables, which will indicate abnormally high or abnormally low changes in laboratory parameter grade based on CTCAE criteria from extension study baseline through extension study follow-up, will be performed by visit.

By-subject listings will be provided for all laboratory data collected, including hematology, chemistry, urinalysis, and pregnancy tests.

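### Abnormalities found only at unscheduled assessments can miss the SAP's by-visit safety tables, which is narrower than Protocol 8.4 promises

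*SAP*

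**What the plan says.** SAP 3.12 has three rules. Data are tabulated under the visit label on the CRF, even if the assessment was out of window. Unscheduled data enter the summaries under a condition: "If the evaluation visit is missing in the database but there are data from an unscheduled or additional visit that is inside the visit window". All available data are listed for each subject.

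The safety sections of the SAP then fix the table layout:

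- Laboratory shift tables (4.5.4) run "from extension study baseline through extension study follow-up, will be performed by visit".
- Injection-site findings (4.5.3) "will be summarized by visit according to severity (none, mild, moderate, severe) and type of reaction". The next sentence says that when a subject has several occurrences of one reaction type, the worst is used.
- ECG shifts (4.5.6) and vital signs (4.5.10) are also by visit.

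Protocol 8.4 says that "all data collected, even if outside of visit windows, will be included in all analyses of endpoints". Laboratory and vital-sign data are to be summarized by time of collection and, in addition, as change from baseline to any value after dosing. It also says: "Frequency of patients with abnormal safety laboratory results will be tabulated". Under Protocol 2.2.1 and SAP 1.4.1, changes in vital signs, laboratory evaluations and injection site reactions are part of the primary endpoint, alongside AEs.

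**The concern.** The protocol deliberately generates safety data between scheduled visits. Section 3.1 allows extra clinic or telephone visits to follow a dose change or an AE. Section 1.1.1 says that adults on the higher dose levels "should be monitored closely via additional unscheduled visits or telephone calls to assess safety and tolerability". Section 6.4.9 allows repeat blood pressure and heart rate after significant increases, and 6.4.11 requires repeat testing of clinically significant laboratory abnormalities. Injection sites are evaluated between visits where warranted (6.4.15) "and in the setting of any injection site reaction adverse experience" (Appendix 11.1).

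These assessments are made because someone suspects or is following a problem, so they are informative about safety. If the summary rule sets them aside whenever the scheduled visit was attended, the tables can undercount patients who ever had an abnormality. That count is part of what the primary objective asks for.

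**Working it through.** There is no stated figure to reproduce. Protocol 8.1 says that "sample size estimation and power analyses are not relevant", and neither document gives an expected number of unscheduled assessments. The check is therefore one of text and logic.

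**Step 1. Apply SAP 3.12 to the possible cases.**

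- Scheduled visit present, plus an unscheduled value: the scheduled value is summarized and the unscheduled value is listed.
- Scheduled visit missing, unscheduled value inside the window: the unscheduled value is summarized.
- Scheduled visit missing, unscheduled value outside the window: the value is listed.

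The word ‘only’ does not appear in 3.12. The exclusion is the natural reading, because the condition would be redundant if unscheduled values were summarized anyway. The text available also gives no numeric visit windows, so the second and third cases cannot be told apart as written.

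**Step 2. Look for another table that would capture the excluded value.** Every visible laboratory, ECG, vital-sign and injection-site summary with a stated time structure is by visit. Two have none stated: the raw and change summary of laboratory values in 4.5.4 and the ECG interval summary in 4.5.6. Neither is described as taking a worst or any-time value, and 3.12 governs both. No visible section defines a worst-post-baseline summary for laboratory, ECG or vital-sign data.

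**Step 3. Compare with Protocol 8.4.**

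- All collected data in all endpoint analyses: the first and third cases above fall short. SAP 3.11 also says that analyses use all available data, so 3.12 sits awkwardly with the SAP itself.
- Change from baseline to any value after dosing, for vital signs and laboratory results: this is promised in addition to the summary by time of collection, and is not clearly carried into 4.5.4 or 4.5.10.
- Frequency of patients with abnormal laboratory results: a series of by-visit shift counts does not give the number of distinct patients with an abnormality, because one patient may appear at several visits or, if abnormal only between visits, at none.

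**Step 4. A constructed example.** Suppose ALT is normal at extension baseline, at V9 (week 104) and at V10 (week 116), but raised at an unscheduled draw between them. The by-visit shift table shows normal to normal at both visits, so this patient contributes 0 abnormal shifts there. A per-patient worst-post-baseline table counts the patient once. The raised value is still listed, and is an AE if judged clinically significant.

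**Step 5. Injection sites.** The worst-occurrence sentence in 4.5.3 could bring an unscheduled evaluation into the table. It does not say whether it does, or under which visit such a finding would fall. This is an ambiguity, not an exclusion.

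**Step 6. Size.** The quantity needed is the number of patients whose abnormality was found only at an unscheduled assessment that 3.12 leaves out. None of its inputs is stated, so no figure is given.

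**The case against.** The strongest reply is that little is lost. Protocol 7.2 makes any clinically relevant deterioration in laboratory or other findings an AE, and 7.2.1 records clinically significant injection-site reactions and laboratory abnormalities as AEs. AEs are graded and collected whatever the visit day, and they are the first component of the primary endpoint. All values are listed. By-visit tables are the protocol's own specification, and they avoid giving extra weight to patients who are measured often. The all-data sentence in Protocol 8.4 could be meant for late scheduled visits, which 3.12 does include. Some SAP text is redacted, so further summaries may exist.

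Much of this stands, and it rules out several stronger conclusions that a reader might draw:

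- That unscheduled data never reach a summary. They do when the scheduled visit is missing and the data are in window.
- That the tables are biased toward normal in general. Repeat tests often follow an abnormality already tabulated at a scheduled visit, and the value dropped may be the more normal one.
- That injection-site reactions count only if present on the visit day. The AE route and the worst-occurrence rule both say otherwise.
- That patients on higher doses lose the most. Section 1.1.1 allows telephone calls, which yield no laboratory, ECG or clinic-measured values.
- That visit spacing gives the size. With visits 12 weeks (84 days) apart and uniform onset, an abnormality lasting 7 days would be present at a visit with probability 7/84 = 8%, and one lasting 60 days with probability 60/84 = 71%. These figures describe how often a quarterly schedule catches a transient event. They do not measure the effect of 3.12, since an event with no unscheduled draw is missed under any rule.

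What the reply does not remove is the gap itself. The AE route depends on the investigator's judgement of clinical significance, listings give no frequencies, and the protocol's per-patient laboratory count and any-post-dose change are separate commitments from the by-time summary.

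**Conclusion.** The point holds in a limited form. On its natural reading, SAP 3.12 leaves a laboratory, ECG or vital-sign abnormality found only at an unscheduled assessment out of the numeric and shift tables, unless the scheduled visit is missing and the value is in window. That is narrower than Protocol 8.4 and can undercount part of the primary safety endpoint. For injection sites the text needs clarifying. The effect cannot be sized from the documents. The conclusion assumes that the condition in 3.12 is meant to be exclusive and that no redacted section supplies a worst-value summary. In a single-arm descriptive study with full listings this does not undermine the trial, but it should be corrected before the tables are produced.

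**What to change.** Keep the by-visit tables on scheduled visits, then make three changes to the SAP:

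- In 3.12, 4.5.4, 4.5.6 and 4.5.10, add a per-patient summary of the worst post-baseline value or grade over all scheduled and unscheduled assessments through follow-up, each patient counted once per parameter. For laboratory data, include the number and percent of patients with any post-baseline abnormality.
- In 4.5.3, add the worst severity per reaction type per patient over the extension, and state that unscheduled evaluations are included.
- In 3.12, say that the missing-visit rule applies to the by-visit tables, and give the visit windows or point to where they are defined.

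The cost is SAP wording and a few extra tables from data already collected. Reported abnormality rates will be somewhat higher than under the by-visit tables alone, and the table notes should say why.

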3.13. Interim Analyses

No formal interim analyses are planned; however, various data cuts may occur in support of regulatory submission such as NDA. The timing of these data cuts and the number of subjects included in each analysis will take into account specific requests from regulatory agencies and applicable regulatory guidance. The rationale for each analysis will be documented.

3.14. Final Analyses

A final analysis will be performed when all subjects complete the study, defined as last subject last visit.

4. STUDY ANALYSES

4.1. Subject Disposition

A tabulation of the disposition of subjects will be presented, including the number enrolled, the total time followed since index study baseline and since extension study baseline, the number of subjects completing the extension study, the number of subjects discontinuing from the study, and the reasons for any subject who discontinued. Disposition will be summarized by index study and overall.

A by-subject data listing of study completion information including the reason for premature study withdrawal, if applicable, will be presented.

4.2. Demographics and Disease Characteristics

Demographics and disease characteristics will be summarized and presented overall and by index study. Age at index study enrollment, country of investigational site, height, weight, BMI, and waist circumference will be summarized using descriptive statistics (number of subjects, mean, standard deviation, median, minimum, and maximum). The number and percentage of subjects in each sex, gene type, ethnicity and race category will also be presented.

Medical history prior to enrollment in index trial and brief medical history collected prior to enrollment into extension study will be included in a by-subject listing, with extension study medical history flagged in the listing.

4.3. Exploratory Evaluations

CONFIDENTIAL

Change and percent change from the index trial baseline as well as change and percent change from the extension study baseline (as defined in Section 3.4). will be summarized for all patients and separately for patients > 18 years of age .

A by-subject listing be provided for all subjects.

Rhythm Pharmaceuticals, Inc. Statistical Analysis Plan, Protocol RM-493-022 June 28, 2024 Version 2.0

4.5. Safety Evaluations

4.5.1. Study Drug Exposure

The duration of exposure in days will be reported for the for both the index + extension studies as wells the extension study only. The duration of exposure for the extension study will be calculated as the extension study last dose date minus the extension first dose date + 1; the duration of exposure for the index + extension studies will be calculated as the sum of the extension period duration (as described above) plus the duration of exposure for the index study (last dose date -1 first dose date +1 from index study). Data will be summarized and listed.

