3.4. Transition into Another Rhythm Trial

Patients enrolled in this extension trial may exit the trial to participate in other setmelanotide clinical trials with the patient's (or legal guardian's) written informed consent, at the discretion of the investigator and sponsor. The patient is to complete the extension Transition Visit prior to commencing treatment in the other setmelanotide clinical trial; applicable data from this visit will serve as Screening data for the other trial. After completion of the Transition Visit, the patient will not need to complete the Early Termination (ET) visit in the extension trial prior to transition to the other trial.

At the conclusion of the other setmelanotide trial, the patient may transition back into this extension trial, again with the patient's written informed consent, at the discretion of the investigator and sponsor, if continuation of setmelanotide treatment is considered beneficial and the patient continues to be eligible for the extension trial. In such cases, the patient will resume the extension trial at the time point/visit at which he or she was at prior to transition to the other trial. Furthermore, after transition back into this extension trial, the patient is to receive setmelanotide at the same dose as they had received prior to transition to the other trial, unless the dose needs to be reduced due to tolerability reasons or in case a dose increased is required for potential additional efficacy needs, at the investigator's discretion. If at the time the patient completes the other setmelanotide trial, setmelanotide becomes commercially available for an indication for which that patient qualifies, the patient will not be eligible to re-enter this extension trial.

If a patient transitions to another setmelanotide clinical trial before completing the ET visit in this extension trial, but does not transition back into this extension trial, the patient will not complete the ET visit or follow-up in the extension trial.

If feasible, patients are to have no interruption in setmelanotide treatment between this extension trial and the other setmelanotide trial. If an interruption in treatment is necessary due to administrative reasons, every effort is to be made to minimize the duration of the interruption and interruptions >21 days are not permissible without prior approval from the sponsor.

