1.2.2. Exploratory Objectives

1.3. Study Design

1.3.1. Synopsis of Study Design

This is a long-term extension study of up to an additional 7 years duration beyond the index trial for patients who have completed a previous study on treatment with setmelanotide for rare

genetic, syndromic, or acquired diseases of obesity upstream of the MC4R in the melanocortinleptin pathway and other abnormalities of the MC4R pathway.

Since continued assessments of the safety and efficacy of setmelanotide are the same in this extension protocol regardless of the index protocol, all patients can be followed consistently in this single extension protocol. The index trials relevant to this study are identified in Table 1-1. Eligible and consenting patients start in the extension trial immediately on the completion of their index protocol (ideally, Visit 1 of this trial will coincide with the final visit of the index trial) in order to limit gaps in treatment.

Patients are assessed approximately every 3 months for adverse events (AEs), concomitant medications, the height (in children),

Patients enrolled in this extension trial may exit the trial to participate in other setmelanotide clinical trials. At the conclusion of the other setmelanotide trial, the patient may transition back into this extension trial. In such cases, the patient resumes the extension trial at the time point/visit at which he or she was at prior to transition to the other trial. Furthermore, after transition back into this extension trial, the patient receives setmelanotide at the same dose as they had received prior to transition to the other trial, unless the dose needs to be reduced due to tolerability reasons or in cases where a dose increase is required for potential additional efficacy needs at the investigator's discretion.

Study Identifier	Study Phase	Number of Subjects who participated in Extension Trial	Diagnosis of Subjects
011	2	9	Genetic disorder of obesity
012	3	13	Early Onset POMC/PCSK1 Deficiency Obesity
014	2	119	Genetic disorder of obesity
015	3	12	LEPR Deficiency Obesity
023	3	38	BBS and AS
030	2	14	Hypothalamic Obesity
034	2	1	Genetic disorder of obesity

Table 1-1Index Studies Currently Included in RM-493-022

Abbreviations: AS=Alstrom Syndrome; BBS= Bardet-Biedl Syndrome; LEPR = Leptin Receptor; POMC = Pro-opiomelanocortin.

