Note: Patients in RM-493-037 were previously enrolled in one of the index studies and RM-493-022 prior to entering the RM-493-037; patients were eligible to reenroll in RM-493-022 after participation in the RM-493-037. These patients are analyzed according to their index trial.

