4.5.10. Vital Signs

Vital signs will be measured as shown in the SOA (Table 1-2). Aside from those used in exploratory evaluation, the raw, change and percent change from extension study baseline of additional vital signs of temperature, heart rate, systolic blood pressure, diastolic blood pressure, respiratory rate will be summarized descriptively by visit. A by-subject listing of all vital signs will be provided.

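### SAP 4.5.1 credits time spent in another setmelanotide trial to RM-493-022 exposure, and does not limit the index term to active drug (minor)

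*SAP*

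**What the plan says.** SAP 4.5.1 reports duration of exposure twice: for the extension alone, and for index plus extension. The extension figure is "calculated as the extension study last dose date minus the extension first dose date + 1". The combined figure adds an index span, printed as "last dose date -1 first dose date +1 from index study". The operator in that bracket is garbled in the text available. The parallel wording suggests last minus first plus 1, and I read it that way. Neither term carries a deduction, and the index term does not mention active drug.

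The same documents provide for leaving and returning. SAP 1.3.1 allows exit to another setmelanotide trial, after which "the patient resumes the extension trial at the time point/visit at which he or she was at prior to transition"; Protocol 3.4 says the same. The note to SAP Table 1-1 names one such trial: "patients were eligible to reenroll in RM-493-022 after participation in the RM-493-037. These patients are analyzed according to their index trial". Protocol 3.4 wants no break in treatment around a transition but foresees that one may occur: "interruptions >21 days are not permissible without prior approval from the sponsor".

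On the index side, Protocol 5.2 describes patients who enter from placebo-controlled, double-blind index trials. SAP 1.3.2 says that all blinded index trials are complete and unblinded for this analysis. SAP 3.4 ties the index baseline to the first active dose. SAP 4.5.1 has no matching restriction.

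**The concern.** Long-term safety and tolerability is the primary objective, and duration of exposure is the figure that tells a reader how long patients were treated in this trial. A first-to-last-dose span works when treatment in the trial is one continuous stretch. Here the plan itself describes patients for whom it is not: they have a first stretch in RM-493-022, a stretch in another protocol, and a second stretch in RM-493-022. The formula merges all three and labels the result extension exposure.

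The days at issue are of three kinds:

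- **Days in the other trial.** If that trial gave setmelanotide, these are exposure to the drug but not exposure in RM-493-022. The error is attribution.
- **Off-drug days around the transitions.** These are not exposure in any trial.
- **Placebo days in a blinded index trial.** These are not exposure, yet they enter the index + extension total if first and last index dose dates are taken as they stand.

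The note that RM-493-037 patients are analyzed under their index trial settles how they are grouped. It does not settle how their time is counted.

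**Working it through.** The plan states no exposure total, so there is no figure of its own to reproduce. The check applies the printed formula to illustrative timelines.

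**Inputs from the documents**

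- Extension exposure = last extension dose date − first extension dose date + 1 (SAP 4.5.1).
- Visit 9 is at the start of Week 104 (both schedules of assessments): (104 − 1) × 7 + 1 = 722 days.
- The longest interruption around a transition without sponsor approval is 21 days (Protocol 3.4).
- Subjects in SAP Table 1-1: 9 + 13 + 119 + 12 + 38 + 14 + 1 = 206.

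**Assumed, because the documents do not say**

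- Time away: 91 to 365 days (about 3 to 12 months).
- Time in RM-493-022: T = 722 days, for the returner and as the cohort mean.
- Placebo time: 91 to 182 days.
- The first dose date stays that of first entry, because a returner resumes the trial.

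**One returner.** With A days away and G off-drug gap days, the span is T + A + G, against T days in RM-493-022. The overstatement is (A + G) / T.

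| Case | Span, days | Overstatement |
|---|---|---|
| A = 91, G = 0 | 813 | 91/722 = 12.6% |
| A = 365, G = 0 | 1087 | 365/722 = 50.6% |
| A = 91, G = 2 × 21 = 42 | 855 | 133/722 = 18.4% |
| A = 365, G = 42 | 1129 | 407/722 = 56.4% |

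The result depends strongly on T. With no gaps:

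- T = 365 (start of Week 53): 91/365 = 24.9% to 365/365 = 100%.
- T = 2150 (start of Week 308): 91/2150 = 4.2% to 365/2150 = 17.0%.

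**Part that is not setmelanotide at all.** If the other trial gave active drug throughout, only the gaps are off-drug: 42/722 = 5.8% for that patient. The rest is real exposure booked to the wrong trial.

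**Pooled.** Total days: 206 × 722 = 148,732. Per 10 returners:

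- No gaps: 910/148,732 = 0.6% to 3650/148,732 = 2.5%.
- Two 21-day gaps: 1330/148,732 = 0.9% to 4070/148,732 = 2.7%.
- The gaps alone: 420/148,732 = 0.28%.

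**Former placebo patient.** With P placebo days and 722 active days over index and extension together, the combined figure is too high by P/722: 91/722 = 12.6% to 182/722 = 25.2%.

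**What the formula does not get wrong.** A gap between the index trial and the extension is not counted, because the two spans are computed separately and then added.

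**The case against.** The strongest reply is that a first-to-last-dose span is a conventional and openly stated measure, that time away may well be time on setmelanotide, and that every duration in the illustration is assumed. Most of this stands. It limits the size and severity of the point. It does not remove it, because no readable passage takes other-trial time out of a figure labelled as extension exposure, or limits the index term to active drug. One could infer active-only from SAP 3.4 or from the section heading, but two programmers could reasonably differ. The garbled bracket is not part of the argument.

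A reader might infer more than the documents support:

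- **That all the time away is false exposure.** It may be real exposure to setmelanotide. Only gaps and placebo days are not.
- **That the plan contradicts its own visit clock.** A returner re-enters at the visit where he or she left, and "All data will be tabulated per the evaluation visit as recorded on the CRF". Visit labels and exposure duration are different quantities, and nothing requires them to agree.
- **That re-enrolment resets the first dose date and loses earlier time.** Both documents say the patient resumes. Protocol 4.3 allows a modified patient number but says the patient can still be tracked across both trials.
- **That adverse events starting while away are dropped.** This would rest on silence in SAP 4.5.2, where part of the text is missing.
- **That every brief interruption must be netted out.** Counting these is within ordinary practice for a span measure.
- **That adverse event rates are biased.** No readable analysis divides events by exposure. Protocol 8.4 permits combining index and extension safety data, but SAP 3.9 generally confines index data to baselines and entry characteristics.

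**Conclusion.** The point holds in a narrow form and is minor. Followed literally, SAP 4.5.1 books time in another setmelanotide trial, with any transition gap, to RM-493-022, and counts index placebo days in the index + extension total. The effect is confined to the exposure summary and listing.

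The size cannot be fixed from the documents, because they do not give the number of returners, the time away, the number of former placebo patients or the placebo durations. Under the assumptions above, the error is substantial for an individual returner and small in the pooled total. For most of those days the correction is to the trial credited, not to whether the patient was on drug.

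**What to change.** In SAP 4.5.1:

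1. Define extension exposure as the sum of the dosing intervals within RM-493-022, excluding the time from exit to re-entry.
2. Report time in other setmelanotide trials on a separate line, so that total setmelanotide exposure can still be read.
3. Count only active-setmelanotide days in the index term, and write the index formula out cleanly. The blinded index trials are already unblinded, so the periods can be separated.

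Three additions are optional and not needed to meet this point. One is deducting other interruptions, as far as the diary records of missed doses in Protocol 5.5 reach the database. The others are a stated rule for adverse events starting while away, and exposure-adjusted incidence.

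The cost is a few lines of SAP text and some programming. The dose dates around each transition are needed, and dosing while away sits in the other trial's data. The visible downside is a smaller extension exposure figure.
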